7.2 Patient Selection and Confidentiality

To ensure poolability of the data from each Investigator, up to 36 patients may be recruited to the study (to obtain a minimum of 17 evaluable images of each tooth population) by five Investigators from four general dental practices. Patients will be identified and selected according to the Inclusion / Exclusion criteria listed below. All patients and / or parent or guardian must provide written informed consent and be willing to adhere to the study schedule, before being entered in to the study.

Patients will be encouraged to complete both Study Visits, however, patients are free to withdraw Consent at any time, irrespective of their initial consent.

Patients may also be withdrawn from the study by the Investigator on the grounds of safety. Any patients who withdraw or are withdrawn from the study will be replaced.

All patients recruited to the study will be identified by a unique study number, comprising the site number and a patient number, to allow any data collected on them to be anonymized. The investigator will maintain a confidential patient identification list of all patients enrolled in the study (by name and patient number). The list will be maintained at the site and will not be retrieved by the Sponsor. There is no randomization required in this clinical study.

7.3 Study Duration

The overall study period is expected to take 10 months - 3 months for Ethics Committee and NHS, R & D approval, 2 to 3 months for recruitment and study procedures, and 4 months for final follow up, data collection and analysis.

7.4 Inclusion and Exclusion criteria

Inclusion criteria

1. Patient must be \geq 6 years old
2. Patient must have one unrestored, accessible, free smooth buccal surface on a canine or incisor, away from the gingival surface identified with no visible lesion (coded ICDAS 0) – ref. table below
and / or
3. Patient must have one unrestored, accessible, erupting or erupted molar or pre-molar with a visible lesion identified (coded ICDAS 2 or 3) in a plaque stagnation area – ref. table below
4. Patient and / or parent or guardian must be willing and able to give written informed consent
5. Patient and / or parent or guardian must be willing and able to adhere to study schedule

Tooth status population	Exemplar tooth type and location	Additional criteria
Sound tooth	Canine or incisor Away from gingival margin	Enamel should be shiny and feels hard and smooth when the tip of a probe is moved gently across the surface
Active Lesion	Erupting or erupted Molars Fissure pits of occlusal surface	Surface of enamel should be whitish/yellowish opaque with loss of luster; feels rough when the tip of a probe is moved gently across the surface. Lesion should be in a plaque stagnation area i.e. pits and fissures; approximately, near the gingival surface below the contact point.
Inactive Lesion	Molars and pre-molars Smooth surface away from gingival margin	Surface of enamel should be whitish, brownish or black. Enamel should be shiny and feels hard and smooth when the tip of a probe is moved gently across the surface. For smooth surfaces, the caries lesion will be typically located at some distance from the gingival margin.

Exclusion criteria

1. Any Patient with recent tooth bleaching (within previous two weeks of imaging with the Calcivis System)
2. Any Patient having on-going re-mineralization treatment including, but not limited to high concentration prescription fluoride toothpaste
3. Any patient with a fixed orthodontic appliance
4. Any patient currently taking part in a clinical research study, or has taken part in a clinical research study in the previous three months
5. Pregnant and / or nursing mothers

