3.4 Study Rationale

Therefore the purpose of this clinical study is to evaluate both the clinical safety and performance of the next generation Calcivis System for identifying active demineralisation on the surfaces of teeth on a patient population \geq 6 years old.

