7. STUDY DESIGN

7.1 Overview

This is a prospective, multi-site, non-randomised, post-approval clinical study to assess the use of the Calcivis System for assessing active demineralization on tooth surfaces of teeth in patients 6 years and older. This post-approval clinical study will be conducted under the controlled conditions of this clinical study plan, on eligible patients, in a general dental practice setting.

From the Expert Paper on Caries Activity Assessment, Longbottom C, 2015 ⁽¹²⁾ it concludes that the prevalence of active lesions found on the occlusal surfaces of erupting teeth is affected by the erupting stage status of the teeth – with the prevalence of active lesions greater in the earlier eruption stages.

As a result of these and similar findings the choice of teeth for identifying visible lesions which are potentially 'active' has been limited to erupting and erupted molars and premolars (in which case occlusal surface must be such that, apart from minimal presence of an operculum over the distal marginal ridge, it is clear of the gingivae (gum)).

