All teeth surfaces to be imaged will be cleaned by the Dentist, by brushing with water or dental paste and rinsing with water and an air-water spray from a conventional dental 3-in-1 device, according to the Tooth Cleaning Protocol (Appendix 2). Patients will be asked to rinse out thoroughly with tap water.

Immediately following thorough air-drying of each tooth surface to be imaged, the Investigator will take a colour photograph with a standard intra-oral camera and record the ICDAS score /activity status.

Preparation Procedures for imaging with the Calcivis device

Care must be taken to ensure the surface of the tooth and surrounding area are free from saliva before imaging by the use of appropriate moisture control aids.

Each tooth will be air-dried for 5 to 10 seconds immediately before application of the disclosing solution and Calcivis System imaging.

Imaging with the Calcivis System

For teeth from each category (no lesions, and active lesions) a maximum of one tooth per patient can be imaged.

If a patient has more than one tooth of a particular category (sound tooth [no visible lesion], or tooth with active lesion) the investigator will use best clinical judgement to choose a tooth that most clearly fits the criteria of that particular population tooth type, for example if there is the choice of 2 teeth displaying lesions considered active, each identical except one of the teeth has a lesion in a plaque stagnation area (e.g. pits and fissures) and one more distant from plaque stagnation area, the tooth with the lesion in a plaque stagnation area will be chosen.

If the first image of a selected tooth is not clear for interpretation, it is acceptable to take a second image of that tooth, however no more than two images of any one tooth can be taken.

Recruitment will be stopped for each Investigator when a minimum of 17 evaluable images (as determined by the Investigators) from each tooth population have been obtained.

After all imaging has been completed, patients will be asked to rinse out with tap water.

Any adverse events observed or volunteered by the patient will be recorded. If appropriate a colour photograph will be taken of the adverse event with a standard intra-oral camera.

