8.5 Independent Investigator Image Review

After all the images have been taken and verified as acceptable by the originating Investigator, and the CRFs collected, an independent review of the Calcivis images will be undertaken to assess the presence or absence of elevated luminescence on the surface to the teeth imaged with the Calcivis System.

This will be carried out by one of the other Investigators as follows:

Site	Original Investigator	Independent Investigator
1	[name]	[name]
1	[name]	[name]
3	[name]	[name]
3	[name]	[name]
5	[name]	[name]

The independent reviewer will be provided with evidence of both the original investigator's decision on tooth classification (i.e. no lesion, or active lesion, based on ICDAS coding / activity status) along with documented evidence of the clinician's intended location for assessment (this is all documented by the original Investigator prior to imaging using the Calcivis System). In addition, photographic evidence of the actual location of the luminescence will be provided. The determination by the independent reviewer will be made off-site, using the visible and Calcivis images along with copies of the original Investigator's documentation. The data from the independent reviewer will be used for the Primary analysis.

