10. STATISTICAL ANALYSIS

10.1 Sample size

The study will assess the agreement between the Calcivis System and dentist rating of suitable teeth in two teeth populations: 'no visible lesions', and 'active lesions'. Based on previous study data and expert opinion, 'No visible lesions' are expected to correspond to 'no luminescence' according to the Calcivis system in at least 70% of cases. Similarly, 'active lesions' are also expected to correspond to 'luminescence' in at least 70% of cases.

Subjects will provide no more than one tooth of each tooth population. The study sample size is calculated in terms of the number of teeth of each tooth population required. The number of subjects required is then *at most* the total number of teeth required.

For the purpose of sample size calculations, the percentage agreement for each of the two tooth populations are jointly considered as measures of agreement. That is, the study will be deemed a success if the percentage agreement in both of the tooth status populations is statistically significant at the 2.5% level when compared to chance agreement (50%).

Expressed in terms of hypothesis tests, the null and alternative hypotheses are:

$$H_0: p_{a,i}=0.5 \text{ vs. } H_1: p_{a,i}>0.5 \text{ for each tooth status population } i$$

where $p_{a,i}$ is the percentage agreement in tooth status population i .

To achieve at least 90% power overall, a power of 94.9% has been used for each tooth status population individually. The planned method of analysis is an exact binomial test and this has been used to derive a required sample size of 81 for each of the tooth status populations. This is the first sample size after which all subsequent sample sizes provide at least 94.9% power.

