## **11.0 Agreement**

The ICDAS defined tooth status (no visible lesions/active lesions) by the original Dentist, and the independent dentist assessment using the Calcivis System (no luminescence/luminescence) will be listed for each tooth.

A table will be presented cross-tabulating the original dentist ICDAS defined tooth status with the independent reviewer Calcivis finding.

Agreement between the ICDAS defined tooth status and Calcivis finding will be summarised using the negative and positive percent agreement as follows:

- The percentage of teeth with no visible lesion that are assessed as showing no luminescence by the Calcivis System (negative percent agreement);
- The percentage of teeth with an 'active lesion' that are assessed as showing

luminescence by the Calcivis System (positive percent agreement).

The hypothesis that agreement is greater than 0.5 will be tested using an exact binomial test and an exact one-sided 97.5% Clopper-Pearson confidence interval will be presented.

Secondary analyses based on imputing all missing data as a disagreement will be conducted, if appropriate.

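### Does taking sound teeth only from the front of the mouth and lesions only from the back undermine the agreement analysis?

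*Protocol*

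**What the plan says.** Inclusion criterion 2 (Protocol 7.4) defines the sound site as a "free smooth buccal surface on a canine or incisor, away from the gingival surface identified with no visible lesion (coded ICDAS 0"). Criterion 3 defines the lesion site as an "erupting or erupted molar or pre-molar with a visible lesion identified (coded ICDAS 2 or 3) in a plaque stagnation area". Protocol 8.2 and SAP 5.2 then limit imaging to these two groups: "For teeth from each category (no lesions, and active lesions) a maximum of one tooth per patient can be imaged". The table in Protocol 7.4 also describes inactive lesions on molars and premolars, but they are neither an imaging category nor an analysis group.

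Protocol 7.1 explains the choice of lesion teeth. Activity is more prevalent at earlier eruption stages, so the choice "has been limited to erupting and erupted molars and premolars". It gives no reason for taking sound sites only from anterior teeth.

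The study rationale (Protocol 3.4) is to evaluate the "next generation Calcivis System for identifying active demineralisation on the surfaces of teeth". The hypothesis in Protocol 10.1 is narrower: "The study will assess the agreement between the Calcivis System and dentist rating of suitable teeth in two teeth populations". SAP 6.0 repeats it.

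For the analysis, SAP 11.0 says: "A table will be presented cross-tabulating the original dentist ICDAS defined tooth status with the independent reviewer Calcivis finding". It adds negative and positive percent agreement, each tested against 0.5 by an exact binomial test.

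**The concern.** Agreement is meant to show that luminescence tracks active demineralisation. Here the two groups differ in three ways at once: lesion status, tooth type and kind of surface. If posterior stagnation areas gave more signal than anterior smooth surfaces for a reason unrelated to lesion activity, both percent agreements would be high and the study would succeed.

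The documents leave room for such a reason. Protocol 5.6 accepts that elevated calcium can have causes other than caries. Protocol 5.7 names saliva and poor solution coverage among the factors that made images uninterpretable in the earlier study.

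The analysis cannot repair this. Table 5 of the SAP splits by ICDAS 0, 2 and 3, which grades severity within posterior lesions only. Listing 9 records tooth and surface, but stratification or adjustment needs overlap between the groups and there is none. At stake is whether a positive result could be read as evidence that the device identifies activity.

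**Working it through.** **1. The plan's sample size.** Inputs from Protocol 10.1: null agreement 0.50, expected agreement 0.70, one-sided 2.5%, exact binomial test, both populations required, 90% power overall.

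- Target per test: √0.90 = 0.9487, given in the plan as 94.9%.
- At n = 81, the smallest r with P(X ≥ r | 0.5) ≤ 0.025 is r = 50, or 50/81 = 61.7%. The actual level is 0.0224.
- Power per population: P(X ≥ 50 | 0.7) = 0.957.
- Both populations, taken as independent: 0.957² = 0.916. Patients may supply one tooth to each group, but dependence cannot lower the joint figure below 2 × 0.957 − 1 = 0.914.

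The figure of 81 reproduces. With the unrounded target of 0.9487 it is the first n from which every larger n qualifies (the lowest later value is 0.9489, at n = 85).

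**2. A signal that depends only on site.** Assume luminescence at 70% of posterior stagnation sites and 30% of anterior smooth surfaces, whatever the activity. Positive agreement is then 70%, and negative agreement is 1 − 0.30 = 70%. These are the planning values, so the chance of success is the same 0.916 at n = 81 (0.900 at 85, 0.946 at 90). This demonstrates that the two explanations cannot be told apart. It does not measure a risk, because the 70% and 30% site rates are assumed.

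**3. What a within-tooth comparison could add.** Suppose the investigator also marked a lesion-free area of the same kind on the lesion tooth, and luminescence was read at both areas. Take an exact one-sided McNemar test at 2.5%, with 70% luminescence at lesion areas and independence within pairs (all assumptions):

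| Pairs | Matched areas at 30% | Matched areas at 50% |
|---|---|---|
| 10 | 0.20 | 0.04 |
| 20 | 0.593 | 0.150 |
| 30 | 0.827 | 0.258 |
| 40 | 0.927 | 0.354 |

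With 40 pairs the Wald 95% half-width is 1.96 × √[(p₁₀ + p₀₁ − d²)/40]:

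- 70% against 30%: p₁₀ = 0.49, p₀₁ = 0.09, d = 0.40, half-width 0.201.
- 70% against 50%: p₁₀ = 0.35, p₀₁ = 0.15, d = 0.20, half-width 0.210.

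A within-pair correlation of 0.4 would raise the 40-pair, 70/50 power from 0.35 to 0.54.

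Under a site-only signal (70% at both areas, 40 pairs) the test rejects 1.5% of the time if reading is unbiased. If sight of the lesion leads the reader to call 20% of the non-luminescent lesion areas positive, the lesion rate becomes 0.70 + 0.20 × 0.30 = 0.76 and rejection rises to 5.5%. At 30% it becomes 0.79 and 9.8%. ICDAS 2 and 3 lesions are visible by definition, so the reader would often know which area holds the lesion.

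A signal tied to any lesion, active or not, would give the same 93% as an activity signal (70/30, 40 pairs). The comparison separates lesion from site. It does not separate active from inactive.

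**The case for a change.** The strongest case for a change accepts that lesions were deliberately taken from posterior teeth and points out that this does not explain the absence of sound posterior sites. Protocol 3.1 presents the difficulty of judging activity status as the clinical need, and 3.4 gives identification of active demineralisation as the purpose, yet the design cannot show that the signal is specific to activity. Under Protocol 8.5 the independent reviewer already receives the intended location, and "photographic evidence of the actual location of the luminescence will be provided". A second mark and a second reading of the same image would need no new patients or images. At the least, one sentence in SAP 11.0 and the report could limit the conclusion.

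Much of this stands. The confounding is complete, it comes from the eligibility criteria, and passing both tests is consistent with the stated purpose without establishing it. The remedies are where the case weakens:

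- A second reading placed before the primary one would apply to lesion teeth only. The two co-primary groups would then be read under different procedures, so the primary data would change even though the tests did not.
- Placing it after the primary reading avoids that, but the reader then knows the classification and the error rate depends on unbiased reading.
- The documents do not say how many lesion teeth have a comparable lesion-free area on the same surface, so power cannot be planned.
- It would need a written amendment under Protocol 14.2, a revised CRF and extra training, for a result that still leaves active and inactive lesions together.
- The limiting sentence would largely restate Protocol 10.1 and SAP 6.0. Only an explicit remark on specificity would be new, and it would change no estimate, test or decision.

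**Conclusion.** The observation is right: lesion status is completely confounded with tooth type and site, and the planned data cannot separate them. It does not call for a change. The hypothesis and success rule claim only agreement with the dentist's classification in two specified tooth populations, and the planned analysis tests exactly that. Protocol 5.6 already presents the device as an aid whose signal has several possible causes, and Protocol 8.4 bars suggesting treatment on the images alone. Choosing clear-cut examples of each group is a fair trade-off for a post-approval agreement study.

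On size, the 91.6% is the planned power restated under assumed site rates. No documented finding shows that luminescence depends on site. Protocol 5.7 says the coverage and saliva problems of the earlier device were addressed in the redesign, and Protocol 8.2 requires saliva control before imaging. The within-tooth comparison has power anywhere from 4% to 93% across the assumed pair numbers and rates, and cannot address activity. A reader of the report should take a positive result as agreement in these two populations, which is how the plan words it.

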Patient Population:	Eligible patients will be recruited from routine, general dental practices who have one unrestored, accessible, free smooth buccal surface on a canine or incisor, away from the gingival surface, identified with no visible lesion (coded ICDAS 0), and / or one unrestored, accessible, erupting or erupted molar or pre-molar with a visible lesion identified (coded ICDAS 2 or 3) in a plaque stagnation area.
Inclusion and Exclusion Criteria	
Inclusion criteria
 
 1. Patient must be \geq 6 years old 2. Patient must have one unrestored, accessible, free smooth buccal surface on a canine or incisor, away from the gingival surface identified with no visible lesion (coded ICDAS 0) – ref. table on page 27 and / or 3. Patient must have one unrestored, accessible, erupting or erupted molar or pre-molar with a visible lesion identified (coded ICDAS 2 or 3) in a plaque stagnation area – ref. table on page 27 4. Patient and / or parent or guardian must be willing and able to give written informed consent 5. Patient and / or parent or guardian must be willing and able to adhere to study schedule 
Exclusion criteria
 
 1. Any Patient with recent tooth bleaching (within previous two weeks of imaging with the Calcivis System) 2. Any Patient having on-going re-mineralization treatment including, but not limited to high concentration prescription fluoride toothpaste 3. Any patient with a fixed orthodontic appliance 4. Any patient currently taking part in a clinical research study, or has taken part in a clinical research study in the previous three months 5. Pregnant and / or nursing mothers

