6. RISKS AND BENEFITS

6.1 Risk Analysis

Extensive risk analyses have highlighted the following potential areas of safety concern (high impact risks):

1. Integrity of the single use Applicators
2. Deterioration of the Disclosing Solution throughout its shelf life
3. Toxicity of the Disclosing Solution
4. Contamination of vial from re-use (multi-use format only)

These are all considered very low likelihood and have all been adequately addressed by:

1. Integrity testing of applicators in addition to breach requiring a triple fault condition in that previous patient would need to be carrying disease, main device would have to not be cleaned between uses and any contaminant on device would need to penetrate to subsequent patients.
2. Extensive stability studies on the Disclosing Solution
3. ISO 10993 compliant pre-clinical toxicological study and recent clinical study on Disclosing Solution shows no sign of toxicity
4. The multi-use reconstituted solution contains an anti-microbial preservative. In addition , wiping top of Photoprotein vial with alcohol wipes between uses and drawing up of photoprotein with single-use syringes.

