6.2 Potential Risks

The Calcivis system has been designed and tested in compliance with ISO 13485 and will only be used by fully trained dental professionals. Any risks associated with the use of the Calcivis System have been analysed as above, and provision made to either reduce or eliminate these risks. Potential risks to the patient include:

- cross-contamination between patients, if not used according to manufacturer's instructions
- hypersensitivity of patient to protein or other components in Disclosing Solution
- over / under application of Disclosing Solution leading to necessity for repeat procedure
- discomfort and / or soft tissue trauma due to presence of intra-oral imaging device in mouth

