9.2 Collection and Reporting of Adverse Events

It is the responsibility of the Investigator at the site to ensure that all adverse events (AEs, SAEs, ADEs, SADEs (ASADEs and USADEs) and device deficiencies) occurring during the course of the study are recorded on the Adverse Event Form. Details recorded should include the following information:

- A description of the event
- The dates of the onset and resolution
- Any action taken
- The outcome
- The relationship to the device
- Whether or not the adverse event is serious
- Whether the adverse events arises from insufficiencies in the IFU
- Whether the adverse event arises from user error

Any adverse events that occur during the course of the study should be treated by established standards of care that will protect the life and health of the study patients.

Adverse events can be observed directly by the site Investigator or staff, or can be spontaneously reported by the patient. In addition each patient should be questioned about adverse events at each study visit. In all cases it is the responsibility of the site Investigator to collect the information and record as outlined above. All adverse events should be followed up for the duration of the study.

In the case of SAEs, SADEs (ASADEs and USADEs) – including those resulting from device deficiencies), these must be reported to the study Sponsor and to the relevant Ethics Committee according to the term of approval and in addition, any local adverse event reporting guidelines should be followed.

Anticipated Adverse Events are as follows:

- Infection due to cross-contamination from other patient
- Irritation / erythema due to reaction to Disclosing Solution
- Hypersensitivity to the Disclosing Solution

- Pain or discomfort due to presence of intra-oral imaging device in mouth
- Damage/ trauma to soft tissue due to presence of intra-oral imaging device in mouth
- Choking hazard from patient biting down on Applicator

Serious Adverse Events, Serious Adverse Device Effects and Unanticipated Adverse Device Effects must be reported to the Sponsor, within 24 hours of becoming aware of the event. In addition a written report is to be provided by the Investigator within 5 working days.

SAEs, SADEs and UDAEs should be sent by email within the specified timelines to:

[contact] and [contact]

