### **10.3 Relevant Medical History**

Details of relevant medical history and medications (known sensitivities or allergies to photoproteins, and use of calcium supplements and antacids) will be listed.

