 6-11 year olds were asked "Did you find seeing the pictures of your teeth and having the dentist explain them to you helpful?"

Table supported by Listing 12

Table 9  
Safety Population

User Questionnaires

Question	Response	Overall (N=XX)
How easy was it to prepare the Calcivis System?	Easy	X ( xx.x %)
	Neither easy nor difficult	X ( xx.x %)
	Difficult	X ( xx.x %)
How easy was it to use the device?	Easy	X ( xx.x %)
	Neither easy nor difficult	X ( xx.x %)
	Difficult	X ( xx.x %)
How would you rate your overall experience with the Calcivis System?	Good	X ( xx.x %)
	Neither good nor bad	X ( xx.x %)
	Bad	X ( xx.x %)
Were the instructions provided sufficient for you to understand how to use the Calcivis System?	Easy	X ( xx.x %)
	Neither easy nor difficult	X ( xx.x %)
	Difficult	X ( xx.x %)

Produced : xxxxxxxx xx:xx (Page xx of yy)

Table supported by Listing 13

Listing 1

Patient

Disposition

Safety

Population

---

Site  
nt

Patie

Informed Consent

Did the

Patient

Date of Completion/

Number	Number	Date	Time	Complete the Study	Withdrawal	Reason for Withdrawal
XX	YY	DDMMYYYY	hh:mm	Yes	DDMMYYYY	
	YY	DDMMYYYY	hh:mm	No	DDMMYYYY	Consent withdrawn by patient
	YY	DDMMYYYY	hh:mm	No	DDMMYYYY	Investigator withdrew patient
	YY	DDMMYYYY	hh:mm	No	DDMMYYYY	Lost to follow-up
	YY	DDMMYYYY	hh:mm	No	DDMMYYYY	Adverse event
	YY	DDMMYYYY	hh:mm	No	DDMMYYYY	Death
	YY	DDMMYYYY	hh:mm	No	DDMMYYYY	Other: XXXXXXXXXX

---

Produced : xxxxxxxxx xx:xx (Page xx of yy)

## Listing 2

Inclusion and Exclusion Criteria  
Safety Population

Site Number	Patient Number	Criterion Type	Criterion Number	Criterion Text	Criterion Response
XX	YY	Inclusion	1	Patient must be $\geq 6$ years old	Yes
			2	Patient must have one unrestored, accessible, free smooth buccal surface on a canine or incisor, away from the gingival surface identified with no visible lesion (coded ICDAS 0) and/or	Yes
			3	Patient must have one unrestored, accessible, erupting or erupted molar or pre-molar with a visible lesion identified (coded ICDAS 2 or 3) in a plaque stagnation area	No
			4	Patient and/or parent or guardian must be willing and able to give written informed consent	Yes
			5	Patient and/or parent or guardian must be willing and able to adhere to study schedule	Yes
		Exclusion	1	Any patient with recent tooth bleaching (within previous two weeks of treatment with the Calcivis System)	No

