			2	Any patient having on-going re-mineralisation treatment including, but not limited to high concentration prescription fluoride toothpaste	No
			3	Any patient with a fixed orthodontic appliance	Yes
			4	Any patient currently taking part in a clinical research study, or has taken part in a clinical research study in the previous three months	No
			5	Pregnant and/or nursing mothers	No

Listing 3  
Safety Population

Population Assignment

Site Number	Patient Number	Population		
		Safety	Agreement	Lesion
XX	YY	Yes	Yes	No visible lesion
	YY	Yes	No	Active lesion

---

Produced : xxxxxxxxx xx:xx (Page xx of yy)

Listing 4  
Safety Population

Protocol Deviations

Site Number	Patient Number	Date of Protocol Deviation	Details of Protocol Deviation	Reason for Protocol Deviation	Date Reported to Calcivis	Action Taken
XX	YY	DDMMYY	XXXXXXXXXX	Informed Consent Process	DDMMYY	XXXXXXXXXX
	YY	DDMMYY	XXXXXXXXXX	Inclusion/Exclusion	DDMMYY	XXXXXXXXXX
	YY	DDMMYY	XXXXXXXXXX	Study Procedure	DDMMYY	XXXXXXXXXX
	YY	DDMMYY	XXXXXXXXXX	Other: XXXXXX	DDMMYY	XXXXXXXXXX

---

Produced : XXXXXXXX xx:xx (Page xx of yy)

Listing 5  
Demography  
Safety Population

Site Number	Patient Number	Date of Birth	Age 	Gender	Race
XX	YY	DDMMYYYY	xx	Male	Hispanic or Latino
	YY	DDMMYYYY	xx	Female	Asian
	YY	DDMMYYYY	xx		Black
	YY	DDMMYYYY	xx		White
	YY	DDMMYYYY	xx		Other: XXXXXXXX

---

Age = (Date of informed consent–Date of Birth+1)/365.25.

Produced : xxxxxxxx xx:xx (Page xx of yy)

Listing 6  
Safety Population

Relevant Medical History and Medications

Site Number	Patient Number	Question	Response	Name	Frequency	Date of Last Dose	Time of Last Dose
XX	YY	Any known sensitivities or allergies to photoproteins?	No				
		Do you take any calcium supplements?	Yes	XXXXXXXX XXXXXX	DDMMYYYY	HH:MM	
		Do you take any antacid tablets?	Yes	XXXXXXXX XXXXXX	DDMMYYYY	HH:MM	

---

Produced : xxxxxxxxx xx:xx (Page xx of yy)

Listing 7 Oral

Hygiene  
Safety Population

Site Number	Patient Number	Question	Response	Details
XX	YY	Which toothpaste do you use most often?	XXXXXXXXXX	
		How many times per day do you brush your teeth?	Once per day Twice per day Three times per day Other	XXXXXXXXXX XXXXXXXXXX
		Do you use mouthwash?	Yes No	XXXXXXXXXX XXXXXXXXXX
		On average, how many times per day do you use mouthwash?	Once per day Twice per day Three times per day Other	XXXXXXXXXX XXXXXXXXXX
		Do you use any other dental products?	Yes No	XXXXXXXXXX XXXXXXXXXX

---

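### No exclusion for known hypersensitivity to the Disclosing Solution, although it is a named risk and photoprotein allergy is recorded before imaging

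*Protocol*

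**What the plan says.** **Eligibility.** Protocol 7.4 has five exclusions: recent bleaching, current re-mineralization treatment, a fixed orthodontic appliance, other research participation, and "Pregnant and / or nursing mothers". The synopsis has the same five (for example "Any patient with a fixed orthodontic appliance"), as does SAP Listing 2, which runs from "Any patient with recent tooth bleaching (within previous two weeks of treatment with the Calcivis System" to "Pregnant and/or nursing mothers". No inclusion criterion mentions allergy.

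**Risk.** Protocol 6.2 names "hypersensitivity of patient to protein or other components in Disclosing Solution" among the potential risks to the patient. Protocol 9.2 includes "Hypersensitivity to the Disclosing Solution" among the anticipated adverse events. Protocol 6.1 adds that "The multi-use reconstituted solution contains an anti-microbial preservative".

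**History.** Protocol 8.2 and SAP 5.2 collect relevant medical history and medications at Visit 1, as pre-imaging information. SAP 10.3 says that this history includes "known sensitivities or allergies to photoproteins", and Listing 6 shows the question with a yes/no response. SAP 10.3 plans only to list the answers.

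**Discretion.** Protocol 7.2 lets the investigator withdraw a patient on safety grounds. It does not link this to any history item.

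**The concern.** The sponsor recognises the hazard and asks a question directed at it, but the plan does not say what follows from a yes. Read literally, a patient who reports a photoprotein allergy meets all the criteria and goes on to have the solution applied, unless the investigator intervenes under a general power or a document outside the protocol and SAP says otherwise. Five investigators could handle the same answer differently.

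The question is also narrower than the risk. An allergy to the preservative or another component falls within the hazard in Protocol 6.2 but would not be elicited by the Listing 6 wording.

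Safety is a primary objective and enrolment starts at age 6, whereas the earlier clinical study described in Protocol 5.7 enrolled patients aged 16 to 25. What is at stake is avoidable exposure of an identifiable patient. The validity of the agreement estimates is not in question.

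**Working it through.** The claim is about text, so the main check sets the provisions side by side.

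| Step | Where | Does it act on a known allergy? |
|---|---|---|
| Inclusion and exclusion criteria | Protocol synopsis and 7.4; SAP Listing 2 | No |
| Risk controls (applicator integrity, stability, toxicology, vial contamination) | Protocol 6.1 | No; none screens the patient |
| History taken before imaging | Protocol 8.2; SAP 5.2 and 10.3; Listing 6 | Photoprotein allergy recorded; no action stated |
| Preparation, cleaning, drying, imaging | Protocol 8.2; SAP 5.2 | No conditional step |
| Withdrawal for safety | Protocol 7.2; SAP 4.0 | General discretion, not tied to the answer |

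One link is inferred. The protocol does not print the allergy question, so its timing before imaging comes from reading Protocol 8.2 together with SAP 10.3 and Listing 6.

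**Exposure.** Protocol 5.5 gives 100 µg/ml and 25 µl per application:

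- per application: 100 µg/ml × 0.025 ml = 2.5 µg, which matches the stated figure;
- minimum per patient: 1 tooth × 1 image × 2.5 = 2.5 µg;
- maximum per patient: 2 teeth × 2 images × 2.5 = 10 µg.

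The per-patient figures use the limits in Protocol 8.2 (one tooth per category, at most two images per tooth) and assume one application per image.

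**Patients affected.** The documents give no prevalence. Assuming 0% to 1%, with the synopsis range of 85 to 180 patients:

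- 85 × 0 to 85 × 0.01 = 0 to 0.85;
- 180 × 0 to 180 × 0.01 = 0 to 1.8.

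**Effect of an added exclusion on the sample size.** The plan's own figure was reproduced first. Protocol 10.1 states 81 teeth per population, using an exact binomial test of 50% against 70% at one-sided 2.5%, with 94.9% power for each population.

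- At n = 81, the smallest r with P(X ≥ r | 0.5) ≤ 0.025 is 50.
- The exact one-sided level is then 0.0224, and power at 70% is 0.957.
- Joint power, if the two populations are independent, is 0.957² = 0.916.
- With the unrounded per-population target √0.90 = 0.9487, 81 is the first n from which power stays at or above target. At n = 80 power is 0.941; at n = 85 it is 0.9489.

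None of these inputs depends on the exclusion list. Recruitment runs until each investigator has at least 17 evaluable images per population, so 5 × 17 = 85 teeth are still obtained, 85 − 81 = 4 above the requirement.

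**The case against.** The strongest reply is that the answer may lie in documents not seen here. The device is CE marked, preparation must follow the Instructions For Use, training covers them, and SAP Listing 8 records whether set-up complied. A contraindication could sit there, or in the CRF, the Patient Information Sheets or the risk report. This limits what can be said about practice: the protocol and SAP are silent, but it does not follow that an allergic patient would actually be treated. It does not answer the eligibility point, because neither document refers to the Instructions For Use for eligibility.

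Second, the dentist takes the history before applying anything and may withdraw the patient for safety, with replacement. That is true and is a real safeguard. It is still not a rule, and it cannot catch an allergy to another component that the question does not ask about. Other provisions, such as rinsing after imaging, treatment of adverse events and safety panel review, are general or act after exposure.

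Third, the evidence is reassuring. The solution had pre-clinical sensitisation testing. In the earlier study of 42 patients the two adverse events were bleeding gums and slight gum abrasion, with no hypersensitivity described. But with 0 events in 42, the exact one-sided 95% upper limit for the reaction rate is 1 − 0.05^(1/42) = 6.9%, and those data do not show what happens in someone with a known allergy.

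Finally, the 0% to 1% prevalence range is an assumption without support in the documents. That stands; the range only illustrates scale.

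**Conclusion.** The concern holds as a minor, optional improvement. On the text of the protocol and SAP, a reported allergy to the Disclosing Solution does not affect eligibility, and the one question asked covers only part of the named risk. Confidence in that reading is high. The practical consequence is less certain: it depends on documents not supplied and on a number of affected patients that may be zero. The point concerns patient safety and changes neither the primary analysis nor the required 81 teeth per population.

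**What to change.** Add a sixth exclusion to the synopsis, Protocol 7.4 and SAP Listing 2: *known sensitivity or allergy to the photoprotein or any other component of the Disclosing Solution*. If the Instructions For Use already state a contraindication, use that wording so that the documents agree. Check the criterion at Visit 1 before any solution is applied; the Schedule of Events already places the eligibility check there. Widen the history question shown in Listing 6, and the matching CRF item, to cover the other components, including the preservative in the multi-use format. The protocol does not name the preservative, so the question should, or patients may be unable to answer.

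The wording is short, but Protocol 14.2 requires a written amendment approved by the sponsor, ethics committee approval where required, and approval from each site's NHS R&D or other local approver before implementation. The form also needs updating. The downside is a very small, unquantified number of patients not enrolled, with no loss of evaluable teeth because recruitment continues to the per-investigator target.
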